6.15.2.1. Common Adverse Events

Common TEAEs are those TEAEs that occurred in $\geq 1\%$ before rounding of total ixekizumab treated patients.

The following summaries (including treatment group comparison) will be provided for common TEAEs based on the safety population for Period 2 and based on Open-label Treatment Population for Period 3:

- Common TEAEs by SOC and PT
- Common TEAEs by PT
- Common TEAEs by maximum severity, SOC, and PT.

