5.3. Determination of Sample Size

The total sample size for the study will be approximately 146 patients randomized at 1:1 ratio in the Blinded Treatment Period to ixekizumab Q2W and placebo (73 patients per treatment group).

No prior static Physician's Global Assessment (sPGA) of Genitalia (primary outcome measure) data was available at the time of planning this study to guide sample size and power calculations because no biologic drug has been evaluated in a well-controlled clinical trial to date in patients with genital psoriasis. Therefore, based on the relevance and impact of sexual impairment in genital psoriasis, data from the assessment of the Dermatology Life Quality Index (DLQI) Item 9 (How much has your skin caused any sexual difficulties?) outcomes in the ixekizumab Phase 2 and Phase 3 studies were used to calculate the sample size. Sample size was calculated assuming sexual impairment rates of 2% and 20% in the ixekizumab Q2W and placebo treatment groups, respectively. With these assumed rates, a sample size of 146 (73 per treatment group) is likely to achieve 94% power, based on a 2-sided Fisher's exact test at 0.05 level of significance.

6. A Priori Statistical Methods

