6.17.2. Safety Subgroup Analyses

Safety subgroup analysis for common TEAEs and AESI of allergy reaction/hypersensitivity and infections will be summarized by treatment group and overall, using the Safety Population for the Blinded Treatment Period (Period 2). The common TEAEs will be presented by MedDRA PT within SOC. The AESI of allergy reaction/hypersensitivity will be presented by anaphylaxis and non-anaphylaxis events, by PT within category. The AESI of infection will be presented by PT.

A logistic regression model with treatment group, subgroup, and the interaction of subgroup-by-treatment group as factors will be used. The subgroup-by-treatment group interaction will be tested at the significance level of 0.10. The response variable will be each AE. Treatment group differences will be evaluated within each category of the subgroup using Fisher's exact test, regardless of whether the interaction is statistically significant. If any group within the subgroup is less than 10% of the total population, only the descriptive statistics will be provided for that subgroup (that is, no inferential testing will be done).

The following subgroups will be analyzed:

- BSA category (<10%, ≥10%)
- Sex (male, female)

- Age category (<40 years, ≥40 years)
- Geographic Region (US, non-US)

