6.19. Clinical Trial Registry Analyses

Additional analyses will be performed for the purpose of fulfilling the Clinical Trial Registry (CTR) requirements. Analyses provided for the CTR requirements include summary of AEs, provided as a dataset which will be converted to an XML file. Both SAEs and ‘Other’ AEs are summarized: by treatment group, by MedDRA preferred term.

- An AE is considered ‘Serious’ whether or not it is a treatment emergent adverse event (TEAE).
- An AE is considered in the ‘Other’ category if it is both a TEAE and is not serious. For each SAE and ‘Other’ AE, for each term and treatment group, the following are provided:
 - the number of participants at risk of an event
 - the number of participants who experienced each event term
 - the number of events experienced.
- Consistent with www.ClinicalTrials.gov requirements, ‘Other’ AEs that occur in fewer than 5% of patients/subjects in every treatment group may not be included if a 5% threshold is chosen (5% is the minimum threshold).
- AE reporting is consistent with other document disclosures such as the CSR.

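### SAP 6.17.2 sets no minimum event count, so in Period 2 it fits treatment-by-subgroup interaction models to adverse-event terms that one ixekizumab patient makes 'common'

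*SAP*

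**What the plan says.** SAP 6.15.2.1 defines the cut: "Common TEAEs are those TEAEs that occurred in $\geq 1\%$ before rounding of total ixekizumab treated patients". Summaries on that basis "will be provided for common TEAEs based on the safety population for Period 2 and based on Open-label Treatment Population for Period 3". SAP 5.3 plans "73 patients per treatment group", and Table RHBQ.6.1 shows a single ixekizumab arm in Period 2.

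SAP 6.17.2 takes these terms, together with the hypersensitivity and infection events of special interest, into a Period 2 subgroup analysis by BSA, sex, age and region: "A logistic regression model with treatment group, subgroup, and the interaction of subgroup-by-treatment group as factors will be used". Each adverse event is a response variable in turn, and the interaction is tested at 0.10. Fisher's exact test is run within every subgroup category whatever the interaction shows. The one restriction concerns subgroup size: a category with less than 10% of patients gets descriptive statistics only. Nothing is said about the number of events, or about whether the interaction test is Wald or likelihood-ratio.

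**The concern.** The word 'common' suggests a screen that leaves terms frequent enough to compare. In an arm of 73 the screen passes anything seen once on ixekizumab, and 6.17.2 relies on it as the gate to a four-cell model with interaction. A term with one, two or three events must leave at least one of the four cells without an event, and the interaction log odds ratio then has no finite estimate. At stake is whether the interaction p-values in the Period 2 safety subgroup output mean anything.

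**Working it through.** **Inputs.** The arm size of 73 comes from SAP 5.3. The stated basis for it holds: at 2% versus 20%, with a two-sided Fisher's test at 0.05, exact enumeration gives 94.7% power and the normal approximation 94.3%, against the stated 94%. The 40:60 BSA split comes from SAP 6.2. The 75:25 and 50:50 splits and all incidences below are assumptions chosen to show a range, since the SAP gives none for adverse events.

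**1. The cut in patients.** 0.01 × 73 = 0.73, so one patient qualifies (1/73 = 1.37%). The same holds for any arm of 100 or fewer. In Period 3, with up to 146 on ixekizumab, 0.01 × 146 = 1.46, so two patients are needed. That falls back to one if 100 or fewer enter.

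**2. What the cut removes in Period 2.** It removes only terms with no ixekizumab patient and at least one placebo patient. With equal incidence p and q = (1 − p)^73, the chance of this is q(1 − q):
- p = 1%: 0.480 × 0.520 = 25%
- p = 2%: 0.229 × 0.771 = 18%
- p = 5%: 0.024 × 0.976 = 2.3%

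**3. Chance that all four cells hold an event.** With n1 + n2 = 73 per arm and equal incidence, this is {[1 − (1 − p)^n1] × [1 − (1 − p)^n2]}². For example, at 5% with 55 and 18: (0.940 × 0.603)² = 0.32.

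| Split per arm | 1.37% | 3% | 5% | 10% |
|---|---|---|---|---|
| 75:25 (55/18) | 1.4% | 12% | 32% | 72% |
| 60:40 (44/29, BSA) | 2.2% | 19% | 48% | 89% |
| 50:50 | 2.4% | 20% | 51% | 92% |

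A term reaches the model only if it is seen on ixekizumab. Dividing by 1 − (1 − p)^73 allows for this: by 0.635 at 1.37% (giving 2.2% to 3.9%) and by 0.976 at 5% (giving 33% to 53%). The picture does not change.

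**4. What the model returns when a cell is empty** (44/29 per arm).
- *One event in all.* The interaction estimate runs from 7.8 to 17.8 to 33.4, and its standard error from 60 to 8,852 to 2.0 × 10⁷, at 10, 20 and 40 iterations. The Wald p-value tends to 1. The likelihood-ratio p-value is also 1.0, because the main-effects model already fits the data perfectly.
- *Two events, one per arm, in opposite BSA categories.* The main-effects model expects 0.5 events in each cell. The likelihood-ratio statistic is 2 × [2 ln 2 + 43 ln(43/43.5) + 28 ln(28/28.5) + 44 ln(44/43.5) + 29 ln(29/28.5)] = 2.80 on 1 df, p = 0.094. The Wald p-value is 0.999 or above.
- *Two events per arm, in opposite categories.* Likelihood-ratio p = 0.017; Wald p again 0.999 or above.

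**The case against.** The strongest reply is that little depends on these p-values. Unfiltered event tables by system organ class and preferred term, with Fisher comparisons in Period 2, are planned in SAP 6.15.2, as is a listing of all adverse events. SAP 6.15.3 adds tables of serious events and of events leading to discontinuation. Fisher's tests run within each subgroup category regardless of the interaction, and no decision rule uses the interaction result. All of this stands, and it limits the impact.

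Four stronger readings are tempting, and the documents do not support them:

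- *The cut removes nothing, so the common tables duplicate the full ones.* It works on ixekizumab patients only, so placebo-only terms drop out at any placebo frequency. In Period 3 it also removes single-patient terms if more than 100 patients enter.
- *Single events create false flags.* They do not: both tests return p near 1. The risk of a spurious flag begins at two events and only with a likelihood-ratio test, which the SAP neither specifies nor rules out.
- *The output can hide a safety signal.* The retained tables, listings and within-category Fisher's tests make that hard to sustain.
- *SAP 6.19 already supplies a 5% definition.* That section sets an optional registry-reporting threshold for non-serious events: "AEs that occur in fewer than 5% of patients/subjects in every treatment group may not be included if a 5% threshold is chosen". It does not define 'common'. Nor would 5% (4 of 73) cure the problem, because at 5% incidence all four cells are filled only 32% to 51% of the time.

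It is also fair to say that no figure in the SAP is miscalculated. It never states a patient count for the 1% cut.

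**Conclusion.** The point holds in this form. In Period 2 the 1% cut is one patient, so it screens out no term seen on ixekizumab. SAP 6.17.2 then prescribes, for every such term and four subgroups, an interaction test that often cannot be estimated. At equal incidence in both arms, at least one cell is empty about 98–99% of the time at 1.37% and 49–68% at 5%, falling to 8–28% at 10%. That amounts to most terms wherever most incidences are at or below about 5%, which is an assumption. For those terms the p-value reflects the choice of test and not the data: near 1 by Wald, and possibly below 0.10 by likelihood ratio on two events.

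This takes the ixekizumab-treated total in Period 2 to be the Q2W arm. If it meant everyone ever treated (up to 146), the cut would be two patients, still too few for four cells. The result does not depend on exactly 73 being dosed, since the cut is one patient for any arm up to 100. The consequence is confined to the Period 2 safety subgroup output.

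**What to change.** In SAP 6.17.2, fit and report the interaction test only for terms with at least one event and one non-event in every treatment-by-subgroup cell. For all other terms, report counts and percentages and keep the within-category Fisher's exact tests, with no interaction p-value. Fisher's tests must stay because an empty placebo cell is what a drug-specific event looks like: 10/36 versus 0/36 in one sex, with no events in the other, gives p = 0.0009, and a counts-only rule would suppress it.

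Optionally, in SAP 6.15.2.1, apply the 'common' cut to either arm, so that placebo-only terms are not left out of a comparative table. The percentage is the sponsor's choice.

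The cost is a few sentences of SAP wording and fewer reported interaction p-values. No events are lost from view. The floor guarantees a finite estimate, not a precise one, so interaction results near it still need cautious reading.

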5.1. Overview of Study Design

Study I1F-MC-RHBQ (RHBQ) is a Phase 3, multicenter, randomized, double-blind, placebo-controlled, parallel-group, outpatient study examining the efficacy and safety of ixekizumab as compared to placebo in patients with moderate-to-severe genital psoriasis. The study consists of 4 periods:

- **Period 1: Screening Period** (Visit 1 and Visit 1A) will assess patient eligibility and start e-diary data collection, occurring approximately 7 to 30 days prior to Period 2 (baseline; Week 0; Visit 2).
- **Period 2: Blinded Treatment Period** will occur from Week 0 (Visit 2) up to Week 12 (Visit 7). Patients will be randomized to ixekizumab or placebo in a 1:1 ratio. Two injections of ixekizumab 80 mg subcutaneous (SC) (total dose of 160 mg) or 2 injections of placebo SC, respectively, will be given at Week 0 (Visit 2). From Week 2 through Week 10 patients will receive ixekizumab 80 mg every 2 weeks (Q2W) SC or placebo Q2W SC.
- **Period 3: Open-Label Treatment Period** will occur from Week 12 (Visit 7) up to Week 52 (Visit 12). At Week 12 (Visit 7) 1 injection of ixekizumab 80 mg SC and 1 injection of placebo SC (total dose of ixekizumab 80 mg) will be given to patients who were randomized to ixekizumab in Period 2; and 2 injections of ixekizumab 80 mg SC (total dose of ixekizumab 160 mg) will be given to patients who were randomized to placebo in Period 2. During the remainder of Period 3, patients will receive ixekizumab 80 mg every 4 weeks (Q4W) dosing with an option to step-up to Q2W dosing starting at Week 24 through Week 40 (at Visit 9 [Week 24], Visit 10 [Week 28], or Visit 11 [Week 40]). This Open-label Treatment Period will allow evaluation of long-term efficacy and safety of ixekizumab through 1 year (52 weeks).
- **Period 4: Post-Treatment Follow-up** (Visit 801 through Visit 803) is for safety monitoring after treatment discontinuation for any patient receiving at least 1 dose of investigational product. Once patients complete the study treatment or discontinue study treatment early, patients will complete the Post-Treatment Follow-up (Period 4). For patients who have entered Period 4, psoriasis therapy is allowed, as determined appropriate by the investigator. This period occurs from the last treatment period visit or early termination visit (ETV) up to a minimum of 12 weeks following that visit.

Figure RHBQ.5.1 illustrates the study design.

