6.1. General Considerations

Statistical analysis of this study will be the responsibility of Eli Lilly and Company (hereafter Lilly). The statistical analyses will be performed using SAS® Version 9.2 or higher.

Change from baseline at a particular visit will be calculated as the value at that visit minus the baseline value.

The means and medians will be reported to 1 more decimal place than the raw data recorded in the database. The standard deviation (SD) will be reported to 2 more decimal places than the raw data recorded in the database. In general, the maximum number of decimal places reported shall be 4 for any summary statistic.

Percentages will be presented to 1 decimal place. Percentages will not be presented for zero counts.

For outcome measures that are not collected at each post-baseline visit, data may exist at visits where the outcome measure was not scheduled to be collected, due to ETVs. In these situations, data from the ETVs that do not correspond to the planned collection schedule will be excluded from any mixed-effects models for repeated measures (MMRM) analysis. However, the data will still be used in other analyses, including shift analyses and other categorical analyses.

General Considerations for Analyses during Blinded Treatment Period (Period 2)

Comparisons of ixekizumab Q2W dosing versus placebo will be performed for all outcome variables in Period 2.

All confidence intervals (CIs) and statistical tests will be 2-sided unless otherwise specified. p-values which are greater than or equal to 0.001, and less than or equal to 0.999, will be presented to three decimal places. All other p-values which are less than 0.001 will be presented as <0.001, while p-values greater than 0.999 will be presented as >0.999. Confidence intervals will be presented to one more decimal place than the raw data.

General Considerations for Analyses during Open-label Treatment Period (Period 3)

Only summary statistics will be presented for the treatment groups:

- Ixekizumab 80 mg, every 2 weeks/every 4 weeks (IXE80Q2W/IXE80Q4W): Patients who received ixekizumab Q2W in the Blinded Treatment Period and ixekizumab Q4W in the Open-label Treatment Period (including those who stepped up to ixekizumab Q2W).
- Placebo/ixekizumab 80 mg, every 4 weeks (PBO/IXE80Q4W): Patients who received placebo in the Blinded Treatment Period and ixekizumab Q4W in the Open-label Treatment Period (including those who stepped up to ixekizumab Q2W).

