- Overall: Unless otherwise specified, no comparisons between IXE80Q2W/IXE80Q4W and PBO/IXE80Q4W will be performed for any outcome variable in Period 3.

Data from patients who step up to ixekizumab Q2W dosing will be included in the efficacy summaries using the Open-label Treatment Population and the treatment groups defined above. The tables, figures, and listings will include footnotes indicating that patients were allowed to increase to Q2W dosing during the Open-label Treatment Period.

The number of patients who step up to Q2W dosing in Period 3 will be summarized by visit and overall using the treatment groups defined above. Patients who step up to Q2W dosing will be flagged in some efficacy and safety listings as deemed appropriate. A separate efficacy listing of sPGA of Genitalia and modified Genital Psoriasis Area and Severity Index (mGPASI) will be provided for patients who step up to Q2W dosing indicating the visits at which the patients started Q2W dosing.

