6.15.3. Deaths, Other Serious Adverse Events, and Other Notable Adverse Events

By-patient listings of deaths, serious AEs (SAEs), and AEs leading to discontinuation will be provided, respectively. All deaths will be included, regardless of the investigator's or the sponsor's judgment about causality, including:

- any deaths occurring during participation in the study in the database for which data are being presented
- any deaths occurring after a patient leaves (is discontinued from or completed) the study in the database for which data are being presented if:
 - the death is the result of a process initiated during the study, regardless of when it actually occurred, or
 - the death occurs during the Period 4 after discontinuation of study drug.

An SAE is any AE that results in one of the following outcomes: death, life-threatening, initial or prolonged hospitalization, disability or permanent damage, congenital anomaly or birth defect, or any other serious/important medical events.

The following summary tables (including treatment group comparison) will be provided for the safety population for Period 2 and the Open-label Treatment Population for Period 3:

- SAEs by PT

- AEs that lead to treatment discontinuation (including death) by PT

A follow-up emergent serious adverse event (FESAE) is defined as an SAE that first occurred or worsened in severity after the date of Visit 12 (that is, Week 52) or the ETV. The following summary tables will be provided for the follow-up population for the Post-Treatment Follow-up Period (Period 4):

- FESAE by PT
- FEAEs that lead to treatment discontinuation (including death) by PT.

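### SAP 6.15.2.1 and 6.15.3 can be read as calling for a between-group comparison of Period 3 adverse events, which the rest of the plan rules out and which could not be interpreted

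*SAP*

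**What the plan says.** Two SAP sections attach a comparison to both treatment periods. SAP 6.15.2.1, on common TEAEs, reads "The following summaries (including treatment group comparison) will be provided for common TEAEs based on the safety population for Period 2 and based on Open-label", and the sentence goes on to name Period 3. SAP 6.15.3, on SAEs by preferred term and on AEs leading to treatment discontinuation by preferred term, reads "following summary tables (including treatment group comparison) will be provided for the safety population for Period 2 and the Open-label Treatment Population for Period 3".

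The general rule for Period 3 in SAP 6.1 is "Only summary statistics will be presented for the treatment groups", followed by "Unless otherwise specified, no comparisons between IXE80Q2W/IXE80Q4W and PBO/IXE80Q4W will be performed for any outcome variable in Period 3". Table RHBQ.6.1 lists no comparison for Period 3 and gives no exception. SAP 6.15, 6.15.2 and 6.15.3.1 place the group comparisons in Period 2 and only summarise Period 3. Table RHBQ.6.6 assigns Fisher's exact test to Period 2 and a summary to Period 3. Protocol 9.6 puts the safety comparison in Period 2 and summarises open-label data separately.

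On dosing at Week 12, SAP 5.1 says "2 injections of ixekizumab 80 mg SC (total dose of ixekizumab 160 mg) will be given to patients who were randomized to placebo in Period", meaning the blinded period, while the other group has been on ixekizumab since Week 0.

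**The concern.** The SAP contradicts itself, and the general rule does not settle the matter. The no-comparison sentence in SAP 6.1 opens with a qualifier that yields to anything specified elsewhere, so a programmer could fairly treat 6.15.2.1 and 6.15.3 as the specified exceptions. An SAE that falls under a special safety topic could then be untested in the Table RHBQ.6.6 output and tested in the 6.15.3 table.

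If the p-values were produced, they would be hard to read. The two groups enter Period 3 at different points in their ixekizumab exposure, and each contains only patients who got through Period 2. A nominally significant result might be reported as a safety difference between starting regimens, when it could reflect only time since first dose or selection.

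**Working it through.** **1. Which passages point which way.** Towards a Period 3 comparison: the parenthesis in SAP 6.15.2.1 and in 6.15.3, supported by the qualifier in 6.1. Against: the summary-only statement in 6.1, Table RHBQ.6.1, 6.15, 6.15.2, 6.15.3.1, Table RHBQ.6.6 and Protocol 9.6. Neither 6.15.2.1 nor 6.15.3 names a test or a contrast for Period 3.

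**2. What Period 3 covers** (SAP 5.1: Week 12 to Week 52, i.e. 40 weeks).

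| Group | First ixekizumab dose | Weeks on ixekizumab inside Period 3 |
|---|---|---|
| PBO/IXE80Q4W | Week 12 | 12 - 12 = 0 to 52 - 12 = 40 |
| IXE80Q2W/IXE80Q4W | Week 0 | 12 to 52 |

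The first 12 weeks on drug are inside one window and outside the other. For a completer in the second group they are 12/52 = 23% of ixekizumab time. By SAP 6.9, Period 2 has 7 injections, and Period 3 on Q4W has 11, of which one (Week 12) is placebo in this group. So 7/(7 + 10) = 41% of that group's ixekizumab injections precede Period 3.

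Two further asymmetries:
- The Open-label Treatment Population (SAP 6.1.1) requires a Period 3 dose, so anyone who stopped in Period 2 is absent.
- SAP 6.15.2 takes pre-treatment severity from before the first dose of the treatment period. An event that arose on ixekizumab in Period 2 therefore counts again in Period 3 only if it worsens.

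**3. How large the distortion could be.** The documents give no AE risk by time on drug, so every risk below is an assumption. Let r1 be the risk of a given term in the first 12 weeks on ixekizumab and r2 the risk over any later 40 weeks, the same in both groups. Then:
- PBO/IXE80Q4W Period 3 risk = 1 - (1 - r1)(1 - r2 × 28/40)
- IXE80Q2W/IXE80Q4W Period 3 risk = r2

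Example: r1 = 15%, r2 = 3% gives 1 - 0.85 × 0.979 = 16.8% against 3.0%.

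The rejection probability is the exact probability that a two-sided Fisher test has p ≤ 0.05, summed over both binomials. It uses 70 per group, an assumed number entering Period 3 from the planned 73. The plan states no figure for this comparison. As a check on the routine, its stated 94% power (73 per group, 2% v 20%) comes out at 94.7%.

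| r1 | r2 | Ratio of weekly hazards, early to late | Period 3 risk, PBO/IXE v IXE/IXE | Fisher rejects |
|---|---|---|---|---|
| 2% | 1% | 6.7 | 2.7% v 1.0% | 0.6% |
| 3% | 1% | 10.1 | 3.7% v 1.0% | 2.3% |
| 3% | 3% | 3.3 | 5.0% v 3.0% | 2.4% |
| 5% | 5% | 3.3 | 8.3% v 5.0% | 5.8% |
| 5% | 3% | 5.6 | 7.0% v 3.0% | 8.1% |
| 8% | 10% | 2.6 | 14.4% v 10.0% | 8.2% |
| 10% | 5% | 6.9 | 13.2% v 5.0% | 28.3% |
| 15% | 3% | 17.8 | 16.8% v 3.0% | 73.6% |

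With constant risk of 5% per 40 weeks (r1 = 5% × 12/40 = 1.5%), the test rejects in about 1.3% of trials.

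A second set of assumptions uses 73 per group and a later risk of 2% per 12 weeks. Rejection is then 5%, 24%, 54% and 79% for early risks of 5%, 10%, 15% and 20%, and 1.9% when risk is constant.

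**The case against.** The strongest reply is that no Period 3 comparison was ever intended. Every passage that assigns a test to AE data assigns it to Period 2, including the parent section 6.15.2. The parenthesis sits ahead of a list of two periods and was probably meant for the first. A reader might infer that the sponsor chose to test the two groups in Period 3; the documents do not support that, because no test, contrast or rationale is given. This stands, and the point is an inconsistency to reconcile rather than a chosen analysis. It does not remove the point: the qualifier in 6.1 leaves the literal reading open, and the Period 4 tables in 6.15.3 omit the parenthesis, which suggests that its scope was not wholly accidental.

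Second, a reader might take the 74% as typical. It needs a term that affects 15% of patients in the first 12 weeks and has a weekly hazard about 18 times the later one. The SAE and discontinuation tables are by preferred term, where such risks are implausible; at assumed risks of 2-3% early and 1% later, rejection is 0.6-2.3%.

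Third, early-exposure events are not lost. SAP 6.15.1 and 6.15.2 provide a Combined Treatment Period with exposure counted from the first ixekizumab dose and an overall AE summary. That is right, but it does not make a Period 3 p-value readable.

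Fourth, treatment in Period 3 is not strictly identical, because the Week 12 dose differs (160 mg against 80 mg plus placebo). After that, both groups follow the same open-label schedule with the same step-up option. The Week 12 difference does not turn the comparison into one the trial was designed to make.

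**Conclusion.** The wording of SAP 6.15.2.1 and 6.15.3 conflicts with the rest of the SAP and with Protocol 9.6 and should be reconciled. Followed literally, it gives p-values in which group is mixed with time since first ixekizumab dose and with selection through Period 2. The exposure offset follows directly from the design. Its effect on a test depends on how strongly events cluster early in exposure, which the documents do not say. With no true group effect and 70 per group, the assumed cases run from about 1-2% rejection for rare terms, through 6-8% for moderate front-loading, to 28-74% for common, strongly front-loaded terms.

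The primary and major secondary efficacy tests and the Period 2 safety comparison are untouched, and no decision rule uses these tables. The severity is minor.

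**What to change.** In SAP 6.15.2.1 and 6.15.3, attach the treatment-group comparison to the Period 2 safety population only. Add that the Period 3 common-TEAE, SAE and AE-discontinuation tables are descriptive, in line with SAP 6.1, Table RHBQ.6.1 and Protocol 9.6. If the two groups are to be shown side by side, tabulate incidence by time since first ixekizumab dose (0-12 weeks, more than 12 weeks), without p-values.

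The cost is two wording edits, plus one extra table if the side-by-side display is wanted. No new data or patients are needed, and all that is given up is a set of nominal p-values with no clear interpretation.
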